## **12 ADVERSE EVENT REPORTING AND ASSESSMENT OF SAFETY**

The safety assessment will be based on the evaluation of AEs that occur from the time of initiation of administration of study drug through 30 days following the last dose of study drug or until the start of a subsequent systemic anticancer therapy (whichever occurs first) and will be determined based on signs, symptoms, physical examination findings, procedure findings, and/or laboratory test results from enrolled participants, as appropriate.

Protocol-related AEs and SAEs will be collected from the time the participant has consented to study participation. AEs and SAEs reported between the time the participant signs the informed consent form (ICF) and the administration of the first dose of study drug will be captured as medical history unless the events are attributed to protocol-specified procedures that are not part of standard of care that occur during this time period, in which case the events will be collected on the Adverse Event CRFs.

SAEs considered related to study drug may be reported at any time, even after the participant's final visit.

Progression of the underlying tumor resulting in hospitalization or death (e.g., participant hospitalized for or dies from progressive disease [PD] only, without any other SAE) will be documented as a tumor response outcome and not as an SAE. If an SAE occurs in a participant and it is unclear whether the event is related to PD, the SAE should be reported.

### **12.1 Definitions**

#### **12.1.1 Adverse Event**

Adverse event means any untoward medical occurrence in a participant or clinical trial participant associated with the use of a drug in humans, whether or not considered drug related. An AE can therefore be any unfavorable and unintended sign (including an abnormal laboratory finding, for example), symptom, or disease temporally associated with the use of a medicinal product, whether or not considered related to the medicinal product.

This includes any occurrence that is new in onset or aggravated in severity or frequency from the baseline condition, or abnormal results of diagnostic procedures, including laboratory test abnormalities.

#### **12.1.2 Adverse Drug Reaction**

Adverse drug reaction (ADR) is a noxious and unintended response to the medicinal product related to any dose. As used herein, the phrase "response to a medicinal product" means that a causal relationship between a medicinal product and an AE is at least a reasonable possibility.

### **12.1.3 Adverse Event of Special Interest**

An adverse event of special interest (AESI) is an event of scientific and medical interest or concern to the sponsor's product or program, for which ongoing monitoring and rapid communication to the sponsor could be appropriate. It may be a serious or non-serious AE, which may require further investigation in order to characterize and understand it; refer to [Section 12.2.4](#) for full details.

### **12.1.4 Attribution/Assessment of Causality**

Attribution/Assessment of Causality is a determination that describes the relationship or association of the study product with an adverse event.

This assessment of causality or relationship of AEs to the study drug is provided by the investigator and is determined by 1) temporal relationship of the event to the administration of study drug; 2) whether an alternative etiology has been identified, and 3) biological plausibility. Causality must be assessed separately for each study drug.

The causality assessment categories that will be used for this study are described below.

Causality assessments that are considered **not related** to study drug:

*None*: The event is related to an etiology other than the study drug (the alternative etiology should be documented in the participant's medical record).

*Unlikely*: The event is unlikely to be related to the study drug and likely to be related to factors other than study drug. An alternative explanation is more likely (e.g., concomitant drugs, concomitant disease), or the relationship in time suggests that a causal relationship is unlikely.

If an SAE is considered "unlikely" or "unrelated" to study drug, the investigator should offer his/her clinical opinion as to what factor(s), agent(s), or process(es) were the likely causative mechanism for the event.

Causality assessments that are considered **related** to study drug:

*Possible*: There is an association between the event and the administration of the study drug and there is a plausible mechanism for the event to be related to study drug; but there may also be alternative etiology, such as characteristics of the participant's clinical status or underlying disease.

*Probable*: There is an association between the event and the administration of study drug; there is a plausible mechanism for the event to be related to the study drug and the event could not be reasonably explained by known characteristics of the participant's clinical status or an alternative etiology is not apparent.

*Definite:* There is an association between the event and the administration of study drug; there is a plausible mechanism for the event to be related to the study drug, causes other than the study drug is ruled out, and/or the event re-appeared on re-exposure to the study drug.

### **12.1.5      Serious Adverse Event**

A SAE is any adverse event that results in any of the following outcomes:

- Death
- Life-threatening (immediate risk of death)
- Inpatient hospitalization for longer than 24 hours or prolongation of existing hospitalization (even if the event is Grade 1)
- Persistent or significant disability or incapacity
- Congenital anomaly/birth defect
- Important medical events

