## 12.2 Adverse Event Collection and Documentation

### 12.2.1 All Adverse Events

All participants who receive at least one dose of study drug will be considered evaluable for safety. AEs will be determined based on signs, symptoms, physical examination findings, and/or laboratory test results from enrolled participants as appropriate.

All adverse events whether serious or non-serious, will be reported from the time a signed and dated ICF is obtained through 30 days following the last dose of study drug or until the start of a subsequent systemic anticancer therapy (whichever occurs first).

Both protocol-related AEs and SAEs will be collected from the time the participant has consented to study participation. AEs and SAEs reported between the time the participant signs the ICF and the administration of the first dose of study drug will be captured as concurrent medical history unless the events are attributed to protocol-specified procedures. Events attributed to protocol-specified procedures will be collected on the Adverse Event eCRFs and SAE Report form as appropriate.

All adverse events, regardless of seriousness, severity, or presumed relationship to study drug, must be recorded using medical terminology in the source document and the eCRF. All records will need to capture:

- the details of the duration, severity, and seriousness of each adverse event
- the action taken with respect to the study drug(s)
- the investigator's attribution/causality assessment concerning the relationship of the adverse event to study therapy
- the outcome of the event

Whenever possible, diagnoses should be given when signs and symptoms are due to a common etiology (e.g. cough, runny nose, sneezing, sore throat, and head congestion should be reported as "upper respiratory infection"). All treatment measures that are required for AE management must be recorded in the source document. The intensity (severity) of AEs will be assessed using NCI CTCAE v4.03 and serious events will be determined by the definition provided in **Section 12.1.5** above. Generally, all non-serious AEs should be entered into the eCRFs within 10 calendar days of the site's awareness.

**Clinical Laboratory Changes:** Safety laboratory assessments will be evaluated by the investigator to ensure participant safety. Laboratory tests will be graded according to NCI CTCAE v4.03. The investigator is responsible for reviewing the results of all laboratory tests as they become available:

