### **12.2.3        Serious Adverse Events**

All SAEs occurring during the study must be reported to the sponsor.

After 30 days following the last dose of study drug administration, if an investigator becomes aware of an SAE that s/he suspects is related to study drug, the investigator should report the event to the sponsor.

Within 24 hours of becoming aware of an SAE, the investigator should provide a completed SAE Report form, via email or fax, to the sponsor. Upon receipt of follow-up information pertaining to an SAE, a follow-up SAE Report form should be submitted to the sponsor within 24 hours of becoming aware of the follow-up information. All SAEs should be entered into the eCRFs within 5 calendar days of the site's awareness.

All Grade 3 or Grade 4 SAEs considered related to study drug must be followed until recovery to baseline or Grade 1.

The investigator must follow all SAEs until resolution and record the date of resolution. Resolution of an event is defined as the return to pre-treatment status or stabilization of the condition with the expectation that it will remain chronic.

All SAEs that have not resolved by the end of the study, or that have not resolved upon discontinuation of the participant's participation in the study, must be followed until any of the following occurs:

- The event resolves
- The event stabilizes
- The event returns to baseline, if a baseline value/status is available
- The event can be attributed to etiology other than the study drug or to factors unrelated to study conduct
- It becomes unlikely that any additional information can be obtained (participant or health care practitioner refusal to provide additional information, lost to follow-up after demonstration of due diligence with follow-up efforts)

Any event requiring hospitalization (or prolongation of hospitalization) that occurs during the course of a participant's participation in a study must be reported as a SAE, except hospitalizations for the following:

- A standard hospitalization for administration of study drug therapy will not be reported as an SAE
- A procedure for protocol/disease-related investigations (e.g., surgery, scans, endoscopy, sampling for laboratory tests, bone marrow sampling, pharmacokinetic or biomarker blood sampling)
- Hospitalizations not intended to treat an acute illness or adverse event (e.g., social reasons such as pending placement in long-term care or hospice facility)

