6.8 Safety Endpoint Analyses

6.8.1 Treatment Emergent Adverse Events

Only TEAEs will be summarized in tables. The following AEs will be provided in summary tables as well as displayed in listings:

- All AEs
- AEs with CTCAE severity grade ≥ 3
- Study drug-related AEs
- Study drug-related AEs with CTCAE severity grade ≥ 3
- SAEs
- Study drug-related SAEs
- AEs that result in discontinuation of study treatment

- AEs that led to dose interruption, dose delay, or discontinuation of individual study drug
- Fatal AEs
- Immediately reportable AEs (if applicable)
- AEs of special interest (AESIs)

All of these tables will display the number and percent of participants that experience the given event and will display events by MedDRA System Organ Class (SOC) and Preferred Term (PT). Events will be displayed alphabetically for SOC and in descending order of overall PT incidence within each SOC. An overall summary of AEs will display the number and percent of participants who experience at least one event of each of the above types.

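### Protocol Sections 12.1.5 and 12.2.3 give opposite SAE status to an unplanned hospital stay of 24 hours or less that is serious on no other ground

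*Protocol*

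**What the plan says.** Protocol Section 12.1.5 lists the outcomes that make an adverse event serious. The hospital criterion is "Inpatient hospitalization for longer than 24 hours or prolongation of existing hospitalization (even if the event is Grade 1"). The same list includes death, life-threatening events, lasting disability, congenital anomaly and important medical events. Section 12.2.1 ties classification to this list: "serious events will be determined by the definition provided in" Section 12.1.5.

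Section 12.2.3 governs reporting. It covers "Any event requiring hospitalization (or prolongation of hospitalization) that occurs during the course of a participant's participation in a study" and says that such an event "must be reported as a SAE, except hospitalizations for the following". Four exceptions follow:

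- "A standard hospitalization for administration of study drug therapy will not be reported as an SAE"
- "A procedure for protocol/disease-related investigations", such as scans or sampling
- admissions that do not treat an acute illness or adverse event, such as placement for social reasons
- surgery or procedures planned before study entry

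Progression of the tumor on its own is also kept out of SAE reporting (Section 12 and the end of Section 12.2.3).

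Table 9 sets the timelines. An SAE needs a form within 24 hours of awareness. Other immediately reportable events need eCRF entry within 24 hours and no form. Non-serious adverse events need eCRF entry within 10 calendar days. Protocol Section 14.7.1 and SAP Section 6.8.1 plan a table of SAEs and one of "Study drug-related SAEs". The SAP does not define the hospital criterion.

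**The concern.** The protocol sends a site to one rule to decide whether an event is serious and to a different rule to decide whether it must be reported as serious. For short admissions the two disagree. Safety is the primary objective, and SAEs are a planned summary of it. If the label depends on which section the investigator reads, the SAE tables do not measure one defined quantity. The reporting timeline, the duty of follow-up and late capture all depend on the same label.

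**Working it through.** The plan gives no figure on this point and no arithmetic is needed. The check sets the two rules side by side and then traces one case through them.

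**Step 1. Where the rules agree.** Both sections count a prolonged existing stay with no time limit. Both count a new admission of more than 24 hours. They can differ only for new admissions of 24 hours or less.

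**Step 2. What drops out of that set.** Three groups get the same answer either way:

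- admissions under one of the four exceptions in Section 12.2.3, none of which depends on length of stay
- admissions for progression alone
- short admissions that are serious on another Section 12.1.5 criterion, such as a life-threatening or important medical event

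**Step 3. What remains.** An unplanned stay of 24 hours or less, to treat an adverse event that is not progression alone and meets no other seriousness criterion. An 18-hour admission for fever is an example, if the investigator judges that no other criterion applies.

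**Step 4. That case under each rule.**

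| Question | Section 12.1.5, through 12.2.1 | Section 12.2.3 |
|---|---|---|
| Is it an SAE? | No | Must be reported as one |
| SAE form within 24 hours? | No | Yes |
| Counted in the SAE tables? | No | Yes |
| Follow to resolution? | No such duty in Sections 12.2.1 to 12.2.4 | Yes |
| Related event first seen after adverse event collection ends (30 days after last dose, or new systemic anticancer therapy if earlier)? | May not be captured | Still reportable if suspected to be related |

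**Step 5. Timing.** The delay depends on Section 12.2.2. Pleural and pericardial effusions, infusion reactions of Grade 3 or higher, immune-related events of Grade 2 or higher and several other categories are immediately reportable whether or not they are serious. They reach the sponsor by eCRF within 24 hours under either rule, although the SAE form, the SAE count and the follow-up duty still differ. For an event in none of these categories, the limit moves from 24 hours to 10 calendar days, a difference of 10 − 1 = 9 days.

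**Step 6. Decisions.** The DLT definitions in Section 4.2 and the escalation counts in Section 4.3 use grade, duration and relation to study drug. Neither uses seriousness.

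**The case against.** The best defence is that the protocol names a controlling definition. Section 12.2.1 points to 12.1.5 for seriousness, and Section 12.2.3 is about reporting, so a site could carry the 24-hour limit over when it reads hospitalization there. Section 12.2.6 also refers to completion guidelines for the SAE form, which are not among the documents and might settle the matter. This offers a possible tie-break but does not remove the conflict. Section 12.2.3 is worded as mandatory, gives its own list of exceptions and makes no reference to the limit.

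The defence is right that the consequences are bounded. The affected events stay in the tables of all adverse events and, where they qualify, in the tables for Grade 3 or higher, drug-related, immediately reportable and special-interest events. No planned decision rule uses an SAE count.

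A reader might also infer that the 24-hour limit clashes with the 24-hour deadline for the form, because length of stay is unknown at admission. The text does not require that reading. The deadline runs from awareness of an SAE, and under 12.1.5 a stay meets the hospital criterion only once it passes 24 hours, so the clock can start then.

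**Conclusion.** The contradiction is real, sits in the current text and needs correcting. It is narrow: it concerns only the admissions left at Step 3. For those, SAE status, the SAE and drug-related SAE counts, the follow-up duty and late capture depend on which section is applied. The reporting delay affects only the part that falls in no immediately reportable category.

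The number of participants involved is unknown. Assuming that 5% to 10% of the planned 182 had a short admission would give 0.05 × 182 = 9.1 to 0.10 × 182 = 18.2, or roughly 9 to 18 participants. That should not be taken as an estimate of the effect. The documents give no such rate, and the calculation removes none of the groups listed at Step 2.

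Two other stronger readings are tempting and unsupported. One is that sites already classify these admissions differently. With about 30 institutions that is foreseeable, but no document reports it. The other is that the SAE count is too low. That assumes Section 12.2.3 is the intended rule, which the documents do not establish.

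**What to change.** Reconcile Sections 12.1.5 and 12.2.3 so that one hospitalization criterion applies throughout. The simplest route that preserves the mandatory wording of 12.2.3 is to remove the 24-hour limit from 12.1.5 and keep the exceptions as listed. If the sponsor intends the limit, 12.2.3 must state it. Either way, check admissions of 24 hours or less already in the database, so that every participant is classified by the same rule before the SAE tables are produced.

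The cost is a wording change, a memo to sites and a one-off query. If the limit is removed, the reported SAE rate may rise slightly.

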### **12.1.6      Severity Criteria**

An assessment of severity grade will be made using the National Cancer Institute Common Terminology Criteria for Adverse Events (NCI CTCAE) Version 4.03 (v4.03). The CTCAE are published standardized definitions for AEs to describe the severity of laboratory and organ toxicity for participants receiving cancer therapy. The investigator should use clinical judgment in assessing the severity of events not directly experienced by the participant (e.g., laboratory abnormalities).

For events not contained in CTCAE, the investigator may assign intensity according to the following generic CTCAE grading scale:

- Grade 1 = Mild; asymptomatic or mild symptoms, clinical or diagnostic observations only; intervention not indicated.
- Grade 2 = Moderate; minimal, local or noninvasive intervention indicated; limiting age-appropriate instrumental activities of daily living (ADL).
- Grade 3 = Severe or medically significant but not immediately life-threatening; hospitalization or prolongation of hospitalization indicated; disabling; limiting self-care ADL.
- Grade 4 = Life-threatening consequences; urgent intervention indicated.
- Grade 5 = Death related to AE.

## 12.2 Adverse Event Collection and Documentation

### 12.2.1 All Adverse Events

All participants who receive at least one dose of study drug will be considered evaluable for safety. AEs will be determined based on signs, symptoms, physical examination findings, and/or laboratory test results from enrolled participants as appropriate.

All adverse events whether serious or non-serious, will be reported from the time a signed and dated ICF is obtained through 30 days following the last dose of study drug or until the start of a subsequent systemic anticancer therapy (whichever occurs first).

Both protocol-related AEs and SAEs will be collected from the time the participant has consented to study participation. AEs and SAEs reported between the time the participant signs the ICF and the administration of the first dose of study drug will be captured as concurrent medical history unless the events are attributed to protocol-specified procedures. Events attributed to protocol-specified procedures will be collected on the Adverse Event eCRFs and SAE Report form as appropriate.

All adverse events, regardless of seriousness, severity, or presumed relationship to study drug, must be recorded using medical terminology in the source document and the eCRF. All records will need to capture:

- the details of the duration, severity, and seriousness of each adverse event
- the action taken with respect to the study drug(s)
- the investigator's attribution/causality assessment concerning the relationship of the adverse event to study therapy
- the outcome of the event

Whenever possible, diagnoses should be given when signs and symptoms are due to a common etiology (e.g. cough, runny nose, sneezing, sore throat, and head congestion should be reported as "upper respiratory infection"). All treatment measures that are required for AE management must be recorded in the source document. The intensity (severity) of AEs will be assessed using NCI CTCAE v4.03 and serious events will be determined by the definition provided in **Section 12.1.5** above. Generally, all non-serious AEs should be entered into the eCRFs within 10 calendar days of the site's awareness.

**Clinical Laboratory Changes:** Safety laboratory assessments will be evaluated by the investigator to ensure participant safety. Laboratory tests will be graded according to NCI CTCAE v4.03. The investigator is responsible for reviewing the results of all laboratory tests as they become available:

- Laboratory values that fall outside of a clinically accepted reference range or values that differ significantly from previous values must be evaluated by the investigator for clinical significance. The investigator may repeat the laboratory test or request additional tests to verify the results of the original laboratory tests.
- A laboratory abnormality should be reported as an AE if it is associated with an intervention. An intervention includes, but is not limited to, discontinuation of treatment, dose reduction/delay, or concomitant therapy. In addition, any medical important laboratory abnormality may be reported as an AE at the discretion of the investigator. This includes laboratory abnormalities for which there are no interventions, but the abnormal value(s) suggests a disease or organ toxicity. If clinical sequelae are associated with a laboratory abnormality, the diagnosis or medical condition should be reported (e.g., renal failure, hematuria) not the laboratory abnormality (e.g., elevated creatinine, urine RBC increased).

**Section 12.2.6** summarizes AE (e.g., SAEs, pregnancy, IREs, etc.) reporting to the sponsor timeframes. The sponsor assumes responsibility for appropriate reporting of AEs to the regulatory authorities. The sponsor will also notify the investigator of regulatory submissions, as appropriate. The investigator is responsible for notifying the appropriate Independent Ethics Committee/Institutional Review Board (IEC/IRB) that approved the protocol, unless otherwise required and documented by the IEC/IRB.

For this study, the participants must be provided with a “wallet (study) card” and instructed to carry this card with them for the duration of the study indicating the following:

- Study number
- Statement, in the local language(s), that the participant is participating in a clinical study
- Investigator's name and 24-hour contact telephone number
- Site number
- Participant number

